11.2 Toxicities of Cisplatin

Nephrotoxicity

A major toxicity of cisplatin is cumulative nephrotoxicity. Tubular necrosis of both proximal and distal renal tubules has been noted in 28-36% of subjects treated with a single dose of 50 mg/m². It is first noted 14 days after a dose and is manifested by elevations in BUN and creatinine, serum uric acid and/or a decrease in creatinine clearance. Renal toxicity becomes more prolonged and severe with repeated courses of the drug. Renal function must return to normal before another dose of cisplatin can be given. Nephrotoxicity can be reduced by IV hydration and mannitol diuresis.

Nausea and Vomiting

Cisplatin causes moderate to severe nausea and vomiting in almost all subjects treated. Nausea and vomiting usually begin within 1 to 4 hours after treatment and lasts up to 24 hours. Various degrees of vomiting, nausea and/or anorexia may persist up to 1 week after the treatment. Delayed nausea and vomiting (beginning 24 hours or more after chemotherapy) has occurred with complete emetic control on the day of cisplatin therapy. The use of prophylactic and continuing antiemetic medication reduces these adverse effects. Subjects should receive prophylactic anti-nausea medications according to ASCO guidelines for highly emetogenic chemotherapy regimens.

Hypomagnesemia

Hypomagnesemia has been reported in subjects treated with cisplatin and is probably related to renal tubular damage. It may become severe enough to cause tetany. Generally, serum electrolytes return to normal levels when cisplatin is discontinued and supplemental electrolytes are administered.

Ototoxicity

Ototoxicity has been observed in up to 31% of subjects treated with a single dose of cisplatin (50 mg/m²) and is manifested by tinnitus and/or hearing loss in the high frequency range (4000-8000 Hz). Decreased ability to hear normal conversational tones may occur occasionally. Ototoxicity can be more severe in children than in adults and more frequent and severe with repeated administration. Hearing loss can be unilateral or bilateral and is usually not reversible.

Myelosuppression

Myelosuppression occurs in 25-30% of subjects treated with cisplatin. The nadirs in circulating platelets and leukocytes occur between days 18 and 23, with most subjects recovering by day 39. Leukopenia and thrombocytopenia are more pronounced at higher doses (>50 mg/m²) than will be administered in this study. Anemia (a decrease in hemoglobin of 2gm.100 ml) occurs at approximately the same frequency and with the same timing as leukopenia and thrombocytopenia.

Neurotoxicity

Cisplatin neurotoxicity is characterized by peripheral neuropathies, which are sensory in nature but can also include motor difficulties such as reduced deep-tendon reflexes and leg weakness. The symptoms usually occur after prolonged therapy (4-7 months). Cisplatin therapy should be discontinued when serious neuropathy develops (defined in Section 4.2.1). The neuropathy, however, may progress further even after discontinuation of treatment.

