4.3 Intervention

4.3.1 Cisplatin Administration

Cisplatin treatment should be initiated following study registration. The starting dose of cisplatin is established as 25 mg/m² ivpb once a week (\pm 3 days) for 1-2 weeks prior to radiation. Dose modification following the first dose of cisplatin is subject to the discretion of the treating physician. Dosing calculation guidelines will follow MSKCC policies described on the website:

http://mskweb5.mskcc.org/intranet/shared/pharmacy/guidelines/Chemo_Guidelines/Manuals/Cisplatin.html

Cisplatin may be initiated immediately following simulation but prior to first radiation fraction. The rationale is so that the patient may initiate a form of treatment while waiting 1-2 weeks for radiation treatment planning to be completed.

Cisplatin may cause myelosuppression or other known non-hematologic toxicities. Following the completion of RT, pending no toxicities, but prior to the week 12 post RT evaluable timepoint, patients will continue to receive cisplatin based on MD discretion, or until POD.

The starting (first) dose of cisplatin will be 25 mg/m² ivpb once a week (\pm 3 days). Following the first dose of cisplatin, a CBC will be drawn once a week (\pm 3 days) prior to treatment to ensure treatment parameters are met. A comprehensive panel and Mg++ level will be obtained on D15 (\pm 3 days) of every cycle of cisplatin; these values will inform the dose for the following cycle of cisplatin. The length of one cycle of Cisplatin is 21 days. If cisplatin is withheld, the cycle count for treatment is also held. Based on the laboratory values drawn from the prior week's bloodwork, if the following parameters are met, cisplatin should be held as directed.

- If ANC is <1,000 mcL and/or platelets are <100,000 mcL, withhold cisplatin therapy for one week and repeat measurements. Physicians have the option of administering growth factor support during the time when ANC < 1,000 mcL or platelets are < 100,000 mcL. The treating MD may modify the subsequent cisplatin doses at their discretion. If there is a delay of 3 consecutive weeks of treatment due to toxicity, then the patient must discontinue protocol therapy and be removed from the study.
- If the ANC is still <1,000 mcL or platelets are 75,000-99,000 mcL, then hold weekly cisplatin again until the ANC is >1,000 mcL and platelets are >100,000 mcL. The treating MD may modify the subsequent cisplatin doses at their discretion.

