- If serum creatinine is >1.5 mg/dL, delay treatment, provide intravenous hydration and check 12 or 24 hour creatinine clearance, serum creatinine and electrolytes after 24 hours. If the serum

creatinine is ≤ 1.5 mg/dL and creatinine clearance ≥ 60 cc/min, may give full dose of cisplatin. If serum creatinine is 1.6-1.9 and creatinine clearance is between 30-60 cc/min, cisplatin can be given at the discretion of the treating physician. If serum creatinine is >2 OR creatinine clearance is <30 cc/min, hold cisplatin.

- If the patient develops any non-hematologic grade 3-4 toxicity, cisplatin will be held until toxicity is reduced to grade 2 or less. Dose reduction is permitted at the discretion of the treating physician. If a patient experiences grade 2 toxicity (with exception of alopecia) that lasts >2 weeks, cisplatin will be held and dose reduction recommended at discretion of the treating physician. Cisplatin will be discontinued if greater than grade 2 toxicity persists following 2 dose reductions.
- If the patient develops an intercurrent illness (e.g. infection) that, in the opinion of the treating medical oncologist, mandates a delay of cisplatin therapy, the intercurrent illness must be resolved within a time frame such that no more than 2 weekly doses of cisplatin are withheld. If therapy must be withheld for a longer period of time, the patient will be removed from the study.
- Following the completion of RT but prior to the week 12 post RT evaluable timepoint, patients will continue receiving cisplatin based on MD discretion. The dose and schedule of cisplatin after the completion of RT will be at the discretion of the treating MD. If there is a delay of 3 consecutive weeks of treatment, then the patient must discontinue protocol therapy and will be removed from study. Continuation of cisplatin and the dose and schedule of cisplatin after Week 12 post RT assessment will be at the discretion of the treating MD.
- Note: Disruption to the cisplatin treatment schedule for 3 weeks due to unforeseen circumstances, holidays or the patient being on vacation is permitted and will be reviewed on a case-by-case basis.

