6.1 CRITERIA FOR SUBJECT ELIGIBILITY

6.2 Subject Inclusion Criteria

- Histologically-confirmed invasive triple negative breast cancer (ER <1%, PR <1%, her-2-neu 0-1+ by IHC or FISH-negative) or as determined by MD discretion
- Radiation to the recurrent or metastatic site is clinically indicated and would be considered standard care for palliation or for locoregional control
- Age \geq 18 years
- Tumor to be irradiated is measurable by RECIST 1.1 or PRC (see Appendix 1 and Section 12.0)
- Willingness to undergo tumor biopsy prior to initiation of treatment
- Life expectancy greater than 6 months
- ECOG performance status 0-2
- Any prior chemotherapy is allowed including prior treatment with platinum-containing chemotherapy
- Prior treatment with FDA-approved or investigational biologics or novel molecularly target therapies, including oral or IV formulations, are permitted. Patients must be off prior targeted therapy for at least 14 days prior to study biopsy.

- Use of an effective means of contraception in women of child-bearing potential
- Ability to comprehend and sign informed consent
- Adequate organ and marrow function within 14 days prior to study entry, defined as:
 - Absolute neutrophil count (ANC)>1000/mm³
 - Hemoglobin >9 gm/dl
 - Platelets >100,000/mm³
 - Serum creatinine <1.5 mg/dl OR creatinine clearance of \geq 50 cc/min
 - SGOT/SGPT<2.5X institutional ULN (<5X ULN if known liver metastases)

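### Sections 11.2 and 4.3.1 disagree on giving cisplatin again while renal function is still abnormal, and the recheck, chemistry-timing and neuropathy wording around them is incomplete

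*Combined protocol and SAP*

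**What the plan says.** **Renal rule, section 11.2.** Under nephrotoxicity: "Renal function must return to normal before another dose of cisplatin can be given". Normal is not defined.

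**Renal rule, section 4.3.1.** The trigger, with its last figure in hours, is "If serum creatinine is >1.5 mg/dL, delay treatment, provide intravenous hydration and check 12 or 24 hour creatinine clearance, serum creatinine and electrolytes after 24". Three outcomes follow:
- Full dose: "creatinine is ≤ 1.5 mg/dL and creatinine clearance ≥ 60 cc/min, may give full dose of cisplatin".
- Discretion: "If serum creatinine is 1.6-1.9 and creatinine clearance is between 30-60 cc/min, cisplatin can be given at the discretion of the treating physician".
- Hold: "If serum creatinine is >2 OR creatinine clearance is <30 cc/min, hold cisplatin".

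**Eligibility, section 6.2.** A patient qualifies with creatinine below 1.5 mg/dL or, alternatively, clearance of at least 50 cc/min.

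**Timing.** Section 4.3.1 bases the hold parameters on bloodwork from the week before. On chemistries it says "A comprehensive panel and Mg++ level will be obtained on D15" (± 3 days) of each cycle and assigns those values to the next cycle's dose. Sections 9.0 and 10.0 repeat the D15 schedule. A cycle is 21 days, with cisplatin on D1, D8 and D15.

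**Neuropathy.** Section 11.2: "Cisplatin therapy should be discontinued when serious neuropathy develops (defined in Section 4.2.1"). Section 11.3 sends the reader to the same number, 4.2.1, for dose modification.

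**The concern.** Section 11.2 is phrased as an absolute condition on re-dosing, while 4.3.1 leaves room to dose below that standard. A physician who relies on one section can give a dose that the other forbids, with a drug whose cumulative nephrotoxicity section 11.2 calls a major toxicity.

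The reading matters beyond the individual dose. Under 4.3.1 and section 13.0, a delay of three consecutive weeks leads to removal from study. Under section 14.0, patients who leave for reasons unrelated to disease are replaced, and a secondary analysis is restricted to those who complete planned treatment. Toxicity is itself a secondary endpoint. Different readings could therefore change who is held, removed and counted. Section 7.0 opens recruitment to all regional sites, so different readings are plausible.

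**Working it through.** The plan states no figure to reproduce here, so the check sets the passages side by side.

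**1. The contradiction.** The discretionary band starts at creatinine 1.6, and 1.6 > 1.5, the level at which 4.3.1 itself delays treatment. The whole band (creatinine 1.6-1.9 with clearance 30-60) is therefore abnormal by the protocol's own trigger. Section 4.3.1 allows a dose there after delay, hydration and recheck; section 11.2 does not. Neither section says which prevails.

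**2. Outcomes on recheck.** Applying the three outcomes of 4.3.1 as written, with creatinine to one decimal:

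| Creatinine (mg/dL) | Clearance <30 | 30 to <60 | exactly 60 | >60 |
|---|---|---|---|---|
| ≤1.5 | hold | **none stated** | full dose | full dose |
| 1.6-1.9 | hold | discretion | discretion | **none stated** |
| 2.0 | hold | **none stated** | **none stated** | **none stated** |
| >2.0 | hold | hold | hold | hold |

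Three regions have no stated outcome. A grid check (creatinine 0.8-2.5 by 0.1, clearance 20-100 by 1) found the same regions and no cell with two outcomes. The bands are thus incomplete but do not overlap. If creatinine is reported to two decimals, values between 1.5 and 1.6 and between 1.9 and 2.0, with clearance of 30 or more, join the list.

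**3. Can patients reach these regions?** Yes. Creatinine 1.7 with clearance 65 satisfies 6.2 on the clearance limb; treatment is delayed, and an unchanged recheck has no stated outcome. Clearance 50 to below 60 also meets 6.2 but cannot meet the full-dose condition of 60 on recheck. For a patient admitted with raised creatinine, a return to normal in the sense of 11.2 has no clear reference point.

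**4. Chemistry timing.** Counting from a D15 chemistry at nominal days:
- next cycle D1 is day 22: 22 − 15 = 7 days;
- next cycle D8 is day 29: 29 − 15 = 14 days;
- next cycle D15 is day 36: 36 − 15 = 21 days. A new panel is due that day, but 4.3.1 assigns it to the following cycle.

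Only the D1 dose of later cycles has a scheduled prior-week creatinine: 1 dose in 3. The ± 3 day windows do not rescue D8, since 14 − 3 − 3 = 8 days. Blood counts are weekly, so the neutrophil and platelet rules are not affected.

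**5. Neuropathy.** Section 11.2 calls for discontinuation on serious neuropathy and points elsewhere for the definition. Section 4.3.1 does not mention neuropathy. Its general rule for non-hematologic toxicity holds at grade 3-4 until grade 2 or less, permits dose reduction, and discontinues if toxicity above grade 2 persists after 2 reductions. Section 13.0 adds removal for grade 4 non-hematologic toxicity, with an exception where the physician sees benefit. None of these says what counts as serious neuropathy.

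**The case against.** The strongest reply is that 11.2 describes drug toxicity and 4.3.1 is the operative rule. Section 11.3, which is about dose delays and modifications, points to 4.2.1, and a reader might infer that the dosing rules are missing because no section has that number. That is not supported. Chapter titles have taken the first subnumber (4.1, 5.1, 6.1, 11.1, 17.1), which pushes subsections down by one; 17.2.1 and 17.2.2 survive under 17.3, and section 14.0 cites 5.4 for immune correlates now in 5.5. The pointer evidently means 4.3.1. This supports the reply, and since 4.3.1 only permits the dose, withholding satisfies both sections. Still, the 11.2 sentence is mandatory in form and no precedence is written down.

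A reader might also infer that the three recheck regions have no rule at all. Two of them lie above 1.5, where the delay already applies; what they lack is a release or hold outcome. The third, low creatinine with clearance below 60, arises mainly at the post-hydration recheck, because 4.3.1 asks for clearance only once creatinine has exceeded 1.5. Section 4.3.1 also leaves dose modification after the first dose to the physician and cites institutional guidelines that are not reproduced, and 6.3 excludes renal dysfunction that would make cisplatin unsafe.

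On timing, section 10.0 allows evaluations as often as clinically indicated, and the D15 panel is a deliberate per-cycle check. One dose in three is therefore a scheduled minimum, not what must happen. The mismatch with the prior-week wording remains.

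On neuropathy, it would be wrong to read 4.3.1 as simply hold and resume, given its discontinuation step and the removal rule in 13.0. The missing definition stands.

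**Conclusion.** The inconsistency is real and should be corrected. It consists of one direct contradiction across the discretionary renal band, three recheck regions without an outcome, a prior-week rule that scheduled chemistries serve for 1 dose in 3, and an undefined neuropathy criterion. This rests on creatinine reported to one decimal, on 4.2.1 meaning 4.3.1, and on the protocol text alone; the cited institutional guidelines might fill some gaps.

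Two stronger conclusions are tempting. The first takes the 28-36% tubular necrosis in section 11.2 as the size of the problem. That figure is for a single 50 mg/m² dose, whereas this trial starts at 25 mg/m² weekly, and it does not measure the effect of inconsistent wording. The second is that the trial's main result is compromised. The documents show a possible route through removals and replacements, but nothing that sizes it. Power does not depend on these passages, and no effect on the comparison of complete response by HRR status is shown.

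**What to change.** - Reconcile 11.2 with 4.3.1 so that one renal rule applies. If normal renal function remains a condition, define it.
- Give every creatinine and clearance result on recheck a stated outcome, including boundary values, and check the result against the eligibility limits in 6.2.
- Make the prior-week bloodwork wording in 4.3.1 agree with the chemistry schedule in 4.3.1, 9.0 and the section 10.0 table.
- Reconcile the neuropathy sentence in 11.2 with 4.3.1 and section 13.0, and define the term it relies on.
- Correct the pointers to 4.2.1 in 11.2, 11.3 and footnote 5 of the section 1.0 schema.

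Which renal rule, neuropathy rule and monitoring schedule apply is for the sponsor to decide. The cost is a wording amendment, with an edit to the section 10.0 table only if the schedule itself changes. Sample size and planned analyses need no change.

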11.3 Dose Delays and Modifications for Cisplatin

See section 4.2.1 for guidelines for dose modification of cisplatin during RT or after RT.

Following the completion of RT, pending no toxicities, but prior to the week 12 post RT evaluable timepoint, patients will continue to receive cisplatin or until POD, based on MD discretion.

11.4 Toxicities of Radiation

Toxicities may occur from radiation treatment. The type and risk of toxicity will depend on the presence of normal tissue structures in close proximity to the target. These normal tissue doses will be constrained by the treatment plan to deliver doses no more than those recommended in our departmental guidelines:

(<http://teamshare/dept/medphys/ebtp/Public%20Documents/Forms/Public%20View.aspx>)

The estimated risk of each type of toxicity is noted below, and include:

1. Skin (erythema, dry or moist desquamation, patchy ulceration) - 40-50%
2. Non-debilitating fatigue- 50%

3. Brachial plexopathy- 5-7%
4. Bowel (bowel perforation, obstruction or hemorrhage) - 2-5%
5. Peripheral nerve (neuropathy or severe neuropathic pain unresponsive to medications)-2-5%
6. Bladder (hemorrhagic cystitis, chronic cystitis manifesting in frequency and urgency) - 2-5%
7. Rectum (injury including ulceration or perforation)-2-5%
8. Osteonecrosis or bone fracture- 5-10%

12.0 CRITERIA FOR THERAPEUTIC RESPONSE/OUTCOME ASSESSMENT

Response to radiation and chemotherapy treatments will be using the Reviewed Response Evaluation Criteria in Solid Tumors (RECIST) guidelines version 1.1 . However there are limitations in using anatomic response criteria alone, particularly when evaluating bone metastases without an extra-osseous component, which is common in breast cancer patients. “PERCIST” (PET Response Criteria in Solid Tumors), is a commonly proposed method for measuring treatment response based on metabolic response criteria with PET [68]. A limitation of PERCIST is that it only takes into account the single hottest lesion and it relies upon SUV peak measurements, which are not easily reproducible in lesions with low FDG-avidity, as are often found in breast cancer. Since there are no standardized methods for quantifying FDG-tracer avidity in individual tumor lesions, we will use a modification of PERCIST criteria called “PET Response Criteria” (PRC) that is currently being utilized in other cancer protocols at MSK requiring metabolic assessment. In brief, the SUVmax of the tumor to be irradiated will be measured and recorded. On subsequent studies, the same target lesion will be measured and recorded. Lesions where SUVmax is no greater than background will be recorded as zero.

Response or progression will be graded as follows:

CR: All lesions no greater than background SUVmax

PR: SUVmax decreased by $\geq 30\%$ greater than background

SD: Lesions that do not fit criteria for response or progression

PD: SUM SUVmax increased by $\geq 30\%$ or development of a new lesion within the radiated field

Radiological review will be conducted by the study radiologists. PET-CT will be obtained in all patients at baseline. In general, PRC will be preferred over RECIST 1.1 for response assessment, except in cases where the tumor target is not clearly defined on PET-CT (e.g. lesions obscured by areas of physiologic FDG-avidity). In such cases, the study radiologists will decide when baseline images are available whether or not to use PRC or RECIST 1.1. If PET-CT evaluation is determined to be insufficient for tumor evaluation, MR will be recommended. The same imaging study (PET-CT or MR) or response criteria (PRC or RECIST 1.1) used at baseline assessment will be utilized for the follow-up assessments of the irradiated tumor.

We anticipate that the most common discrepancy between PRC and RECIST 1.1 will be when there is a CR on PRC, but PR on RECIST 1.1. In these cases, PRC will be utilized for response

assessment. If PRC will be used, RECIST 1.1 is not required for the primary endpoint. However, for the secondary endpoints of comparing PRC to RECIST 1.1, RECIST 1.1 measurements will be done on the CT portion of the PET/CT.

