³ Radiation dose will be $250 \text{ cGy} \times 15 \text{ fx} = 3750 \text{ cGy}$ to the metastatic site delivered in 3 weeks for metastatic disease or $200 \text{ cGy} \times 25 \text{ fx} = 5000 \text{ cGy}$ delivered in 5 weeks to the chest wall, breast and/or regional lymph nodes, plus an optional 10-14 Gy boost to areas of gross tumor, for non-metastatic/locally recurrent disease.

⁴ The length of one Cisplatin cycle is 21 days. If cisplatin is withheld, the cycle count for treatment is also held.

⁵ Cisplatin will be once a week (± 3 days). The dose of cisplatin can be reduced in the event of toxicities defined in Section 4.2.1.

⁶ Following the completion of RT, pending no toxicities, but prior to the week 12 post RT evaluable timepoint, patients will continue to receive cisplatin or until POD, based on MD discretion.

⁷ At 12 ± 2 weeks after RT, all patients will receive PET-CT for treatment response and/or staging. MR will also be obtained if the patient had an MR at baseline.

⁸ PET-CT +/- MR will occur at 12 ± 2 weeks after RT. PET/CT +/- MRI q6 months after RT is recommended but not required.

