2.0 OBJECTIVES AND SCIENTIFIC AIMS

The primary objective of this trial is to evaluate the performance of the MSK-HR repair assay as a biomarker in predicting response to concurrent cisplatin and RT in breast cancer patients with measurable metastatic or unresectable, locally advanced disease. Radiographic complete response (CR) of the irradiated tumor will be counted as a positive response to treatment. Radiographic response less than a CR, progression of the irradiated tumor or appearance of a new lesion within the irradiated field will be categorized as a failure to respond to treatment. All other sites of metastatic disease that is outside of the irradiated field will be monitored and counted toward disease progression.

Secondary objectives are to assess:

- Partial response, stable disease and progression of disease within the irradiated tumor as well as systemically (in sites distant to the irradiated tumor)
- Overall time to progression
- Toxicities of concurrent cisplatin and radiation

Exploratory objectives are to assess:

- Examine immune correlates to determine the impact of treatment on anti-tumor immunity and as a predictor of treatment response
- Determine the sensitivity of ctDNA detection in patients receiving chemoradiation for metastatic and locally recurrent TNBC
- Compare the efficacy of RECIST 1.1 vs. PET Response Criteria (PRC) as measurement tools for treatment response

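### Section 12.0 records SUVmax for one target tumor but grades CR on all lesions and PD on a sum, so the primary outcome is ambiguous when the target clears and another pre-existing lesion stays avid

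*Combined protocol and SAP*

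**What the plan says.** Section 12.0 prefers PRC to RECIST 1.1 unless the target is poorly defined on PET-CT, and lets PRC prevail when it shows CR and RECIST 1.1 shows PR. PRC therefore decides the primary outcome for most patients.

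The measurement text is singular: "the SUVmax of the tumor to be irradiated will be measured and recorded. On subsequent studies, the same target lesion will be measured and recorded". The next sentence turns plural: "Lesions where SUVmax is no greater than background will be recorded as zero". The grading lines stay plural for CR, "CR: All lesions no greater than background SUVmax", and use a total for PD, "PD: SUM SUVmax increased by" 30% or more. The PR line names SUVmax without saying of which lesion. Only the new-lesion clause of PD is limited to the field. The section ends by applying the chosen criteria to follow-up of the irradiated tumor, again singular.

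Section 2.0, repeated in section 14.0, states the primary endpoint: "Radiographic complete response (CR) of the irradiated tumor will be counted as a positive response to treatment". Less than CR, progression of the irradiated tumor, or a new lesion in the field is a failure. Metastatic sites outside the field count toward disease progression. Section 14.0 adds that progression outside the irradiated tumor before the response evaluation is a failure in the primary analysis.

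Fields with more than one lesion are foreseen. Footnote 3 of the section 1.0 schema describes non-metastatic or locally recurrent disease treated "to the chest wall, breast and/or regional lymph nodes", with an optional boost to areas (plural) of gross tumor.

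**The concern.** A sum cannot be formed from one recorded value, and a rule about all lesions cannot be applied if only the target is followed. The reader must decide which lesions count, and the plan does not say. That choice fixes the binary primary outcome in some patients, and nothing prevents it from being made with the week-12 scan in view.

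Two further consequences follow. First, HRR status is measured on the tumor that is biopsied and irradiated (sections 1.0, 4.2 and 5.3). A CR rule that extends to other lesions tests the assay partly against tissue that was not assayed. Second, the CR line is not confined to the field. Read literally, a metastatic patient with stable, avid disease elsewhere could never be a PRC complete responder, although section 2.0 counts such sites only toward progression.

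**Working it through.** **1. Where the readings diverge.** Three readings are possible: (T) the target tumor only; (F) all lesions in the field; (L) all lesions anywhere, as the CR line literally says.

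| Finding at 12 ± 2 weeks | T | F | L |
|---|---|---|---|
| Every lesion at background | CR | CR | CR |
| Target above background | Failure | Failure | Failure |
| New lesion in the field | Failure | Failure | Failure |
| Target clears, another pre-existing in-field lesion avid | **CR** | **Failure** | **Failure** |
| Target and field clear, stable avid disease outside the field | **CR** | **CR** | **Failure** |
| Progression outside the field before evaluation | Failure (section 14.0) | Failure | Failure |

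Only the fourth and fifth rows depend on the reading.

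**2. The PD line.** In the primary analysis anything short of CR is a failure. A growing target offset in a sum by a shrinking node is PD or SD depending on the reading, but a failure either way. The sum can change only the secondary response categories.

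**3. Weight of one patient.** Inputs from section 14.0: N = 54, 40% HRR-deficient.
- HRR-deficient: 0.40 × 54 = 21.6, about 22 patients. One patient is 1/22 = 4.5 points.
- HRR-proficient: 54 − 22 = 32 patients. One patient is 1/32 = 3.1 points.

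The planned difference is 65% − 30% = 35 points.

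**4. The plan's own power.** Two-proportion normal approximation with unpooled variance, one-sided 5%:

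power = Φ( (p1 − p2) / √[p1(1 − p1)/n1 + p2(1 − p2)/n2] − 1.645 )

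At 40% deficient, n1 = 21.6 and n2 = 32.4. The standard error is √(0.2275/21.6 + 0.21/32.4) = 0.1304, and Φ(0.35/0.1304 − 1.645) = 85.0%. At 35% and 30% deficient the results are 83.2% and 80.4%. These match the stated 85%, 83% and 80%, so the power table is not in dispute.

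**5. Illustration only.** The documents give neither the share of patients with several avid lesions nor the share of target CRs accompanied by another avid lesion. Assume that 65% and 30% describe target-tumor CR, and that the same fraction of target CRs becomes failure in both HRR groups under an all-lesions rule. Expected target CRs at 40% deficient are 0.65 × 21.6 + 0.30 × 32.4 = 14.04 + 9.72 = 23.8.

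| Target CRs rescored (assumed) | Patients | CR rates | Power, 40% deficient | Power, 30% deficient |
|---|---|---|---|---|
| 0% | 0 | 65% vs 30% | 85.0% | 80.4% |
| 5% | 1.2 | 61.75% vs 28.5% | 81.3% | 76.1% |
| 10% | 2.4 | 58.5% vs 27% | 77.3% | 71.6% |
| 20% | 4.8 | 52% vs 24% | 68.8% | 62.7% |
| 30% | 7.1 | 45.5% vs 21% | 60.1% | 54.0% |

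The patient counts are 23.8 times the assumed fraction and apply to 40% deficient.

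**The case against.** The strongest reply is that the text can be reconciled. Section 12.0 records one lesion and closes on the irradiated tumor. With one lesion recorded, all lesions and the sum both reduce to it, and sections 2.0 and 14.0 say the same. The section also presents its text as a brief account of criteria used in other protocols at the institution, which may be fuller. This stands in part: the conflict lies first inside section 12.0. It does not settle the matter, because section 12.0 also faults PERCIST for considering only the single hottest lesion, which points toward several lesions.

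A reader might infer that any patient with several in-field lesions is a CR under section 2.0 and a failure under section 12.0. The documents do not support that. The readings part only when the target clears and another pre-existing lesion does not. Section 2.0 never says that the irradiated tumor means the biopsied lesion; it could mean all irradiated gross disease, and then it agrees with an in-field all-lesions rule. The narrower meaning is more natural, since sections 1.0, 4.2 and 5.3 use the tumor to be irradiated for the lesion biopsied, and section 2.0 distinguishes tumor from field. It remains an inference.

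The argument from unassayed tissue also has limits. Section 14.0 already counts progression outside the irradiated tumor as failure, so the endpoint is not confined to assayed tissue. Finally, section 5.3 restricts HRR results to the statistician and principal investigator. The documents therefore show discretion in scoring, not bias toward one HRR group.

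**Conclusion.** The inconsistency is real and should be corrected. The CR line of the preferred criterion does not match the lesion measured or, read literally, the primary endpoint in sections 2.0 and 14.0. It leaves the primary outcome open for patients whose target clears while another pre-existing lesion stays avid, whether in the field or, on the literal reading, stable outside it.

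The size is known per patient: 4.5 or 3.1 points, assuming 40% HRR-deficient among 54. The number of such patients cannot be obtained from the documents, and any count or loss of power rests on assumed rates. The power illustration shows only that the design has little margin: at 40% deficient, rescoring one target CR in ten takes 85.0% to 77.3%. It is not an estimate. A reader might also infer that the PD sum alters the primary result; it cannot, because every outcome short of CR is already a failure.

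**What to change.** In section 12.0, use one unit of assessment for CR, PR and PD: the irradiated target tumor whose SUVmax is recorded, identified as the tumor biopsied for HRR status. Replace the all-lesions and sum wording accordingly and keep the clause on a new lesion in the field. Use the same definition in sections 2.0 and 14.0. Report CR of all in-field lesions as a supportive analysis.

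If the sponsor intends the endpoint to cover all gross disease in the field, it should say so in all three sections and limit the CR line to the field. Either choice should be fixed before outcomes are compared by HRR status.

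The cost is wording in three sections, a reading of other in-field lesions on scans already obtained, and one supportive table. The drawback of the target-only definition is that the headline CR rate describes the target tumor and not the whole irradiated volume.
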